**SPECIFIC AIM 3. Identify if mitochondrial and extra-mitochondrial oxidation of the HF-challenge mediates the relationship between CRF and metabolic health.** In fasting plasma, we will profile the homeostatic model assessment for IR (HOMA-IR), hemoglobin A1c (HbA1c), and a continuous metabolic syndrome score (cMetS), composed of waist circumference (WC), mean arterial blood pressure (MAP), HOMA-IR, HDL-C, and triglycerides (TG) (13). Linear regression will assess the relationship between VO2 max and the metabolic markers. Mediation analyses will be used to identify if FA oxidation metabolite and gene (1) absolute levels, (2) longitudinal trajectories, and (3) ratios (12) mediates the relationship between VO2 max and the metabolic markers, considering the influence of age, sex, pubertal status, and BMI percentile.

The proposed aims will identify modifiable behaviors associated with CRF in youth and will assess if FA metabolism mediates the relationship between CRF and metabolic health, with the long-term goal of developing clinical interventions aimed at improving CRF in youth to preserve metabolic health (Figure 1).

**Figure 1.** Children (BMI%≥5%) will be recruited (aged 8-17). Assessment of characteristics will include blood sampling (glucose homeostasis), a treadmill maximal aerobic capacity assessment (VO2 max), anthropometrics (height, weight, bioelectrical impedance, waist circumference), 24-hr dietary recall, and habitual physical activity measured by an accelerometer. Individuals will undergo a high-fat meal challenge (15% carbohydrates, 15% protein, 70% lipid) and blood sampling will be collected on an acute time-course.

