## 3.0 Background\*

PROTOCOL TITLE: Metabolic Response to a High-Fat Challenge in Children and Adolescents.

Cardiorespiratory fitness is the capacity of respiratory and circulatory systems to supply oxygen to skeletal muscle during exercise for the generation of energy. Beginning in childhood, CRF is predictive of IR and T2D (1), CVD (2), and academic performance (14). There is an intrinsic, nonmodifiable aspect of CRF, influenced by genetics (15, 16), age (17), and sex (18). However, in the past three decades, adolescent CRF has declined (19), with only 40% of youth in the United States (aged 12-15 years) maintaining a healthy CRF (4). Global alterations in behaviors may be influencing the decline in CRF, including increased sedentary time (5), decreased moderate-to-vigorous activity (5), increased obesity (6), and lower dietary quality (7). The American Heart Association (AHA) has recently issued a statement (20) emphasizing the importance of accurately and reliably measuring CRF “to identify youth who would benefit from lifestyle interventions but may have been missed by subjective PA recall, anthropometric measures, or CVD risk factor testing, which are current standards of care.” Profiling maximum oxygen consumption ( $\text{VO}_2\text{max}$ ) during intense exercise is the gold standard measure of CRF. The first objective of this grant proposal is to measure  $\text{VO}_2\text{max}$  using a treadmill protocol and to assess the relationship between CRF and body composition, daily PA, and habitual dietary intake (**Specific Aim 1**), with the long-term goal of developing clinical interventions aimed at improving CRF in youth to preserve metabolic health. There have been no studies to date that considered the cross-sectional interaction between PA, measured by Actigraph accelerometers, and habitual dietary intake, measured by the HEI score (10), on CRF in youth (20). We will consider if the interaction between PA and HEI score modifies the association between percent fat mass and CRF, providing avenues for lifestyle changes in adolescents with overweight and obesity.

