**Protocol – Two Study Visits**

**Study Visit 1:** Participants will arrive at the Clinical Research Unit in Faulkner Building 4M at the Main Campus of Dartmouth Hitchcock Medical Center (DHMC) following a two-hour fast. Consent and assent documents will be available to re-read prior to study visit. A sample of the HF-challenge liquid shake will be available to taste to determine if the adolescents will be willing to participate in Study Visit 2. The CRC or other study team member will collect weight, height, blood pressure, and waist circumference. Each participant will have body composition analyzed using bioelectrical-impedance analyses (BIA).

The CRC or other study team member will transfer the participants and their Parents/Guardians to the Sports Cardiology Unit in Cardiac Services 4A at the Main Campus of DHMC. The CRC or other study team member with CPR and BLS training will acclimate the participant to a treadmill and metabolic cart to undergo a maximal aerobic capacity test, measuring CRF. The maximal aerobic capacity test will use the Bruce Protocol (1), a treadmill multistage incremental protocol. Parents/Guardians will fill out electronic questionnaires about demographics, diabetes family history, and past medical history. Children will fill out electronic questionnaires about puberty status measured by Tanner's Stages.

Participants will be compensated \$25 for the completion of the study visit.

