### **Surveys**

Parents/Guardians will be asked to fill out electronic questionnaires about demographics, diabetes family history, and past medical history. Children will be asked to fill out surveys about puberty status using the Pubertal Development Scale (35) and a taste preference survey after the high fat shake.

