### **Exclusion Criteria**

Previous diagnosis of type 1 or 2 diabetes. Use of concurrent medications known to affect glucose metabolism (metformin, oral steroids, sulfonylureas, insulin). Evidence of inherited disorders of lipid metabolism. Inability to participant in the maximal aerobic capacity test on the treadmill. Allergies to palm oils or protein types within high-fat challenge, such as lactose and soy. Individuals who cannot speak and/or write in English.

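### Diabetes family history is collected for every child but enters no model, so inherited risk may be partly attributed to CRF or fat oxidation

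*Combined protocol and SAP*

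**What the plan says.** Family history is requested in three places in Section 6.0 of the combined protocol and SAP: the two-visit protocol ("Parents/Guardians will fill out electronic questionnaires about demographics, diabetes family history, and past medical history"), the same sentence in the one-visit protocol, and the Surveys subsection ("Parents/Guardians will be asked to fill out electronic questionnaires about demographics, diabetes family history, and past medical history"). It is not mentioned again in Section 2.0 (Objectives) or Section 4.0 (Study Endpoints).

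The adjustment set is in Section 2.0. The Aim 2 mixed models and the Aim 3 mediation analyses are each to be run "considering the influence of age, sex, pubertal status, and BMI percentile". The Aim 3 total-effect sentence, which begins "Linear regression will assess the relationship between" and goes on to VO2max and the metabolic markers, names no covariates of its own.

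Section 3.0 (Background) says: "There is an intrinsic, nonmodifiable aspect of CRF, influenced by genetics". The same sentence adds age and sex as determinants. Age and sex are in the models, but nothing standing for genetics is.

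The Exclusion Criteria remove children with "Previous diagnosis of type 1 or 2 diabetes". Children with affected relatives remain eligible, so family history can vary within the sample.

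**The concern.** CRF is a measured characteristic, not an assigned treatment, so Aims 2 and 3 depend on covariate adjustment. Mediation depends on it three times over: for CRF with the outcome, CRF with the mediator, and the mediator with the outcome. Of the items collected, diabetes family history lies closest to inherited risk for HOMA-IR, HbA1c and cMetS. It is also fixed before CRF is measured, so adjusting for it should not remove an effect that runs through CRF.

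The stated long-term goal is to improve CRF in order to protect metabolic health. If some of the CRF association is inherited background, the part that could be modified is smaller than the unadjusted slope suggests.

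**Working it through.** The plan gives no alpha, power, effect size or SD, so there is no stated figure to reproduce. The calculation below is illustrative.

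**From the documents.** n = 50 (Study Summary; 25 with overweight or obesity and 25 lean in Section 12.0) and four covariates (Section 2.0).

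**Assumed.** Two-sided alpha of 0.05; all 50 children have a VO2max value; no true CRF effect; family history present in a proportion p = 0.25 or 0.40; CRF lower and the marker higher by d = 0.4, 0.6 or 0.8 within-group SD in those children; the four covariates unrelated to family history.

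**Bias.** Let v = d²p(1−p). Leaving family history out gives a spurious slope of −v/(1+v). CRF and the marker have equal variance here, so the spurious correlation r has the same size.

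**False-positive rate.** With k = 4 covariates, Fisher's z has mean m = atanh(r) × √(50−4−3) = atanh(r) × 6.557. The rejection rate is 1 − Φ(1.96−m) + Φ(−1.96−m).

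| p | d | v | slope | false positives |
|---|---|---|---|---|
| 0.25 | 0.4 | 0.0300 | −0.029 | 5.4% |
| 0.25 | 0.6 | 0.0675 | −0.063 | 7.0% |
| 0.25 | 0.8 | 0.1200 | −0.107 | 10.9% |
| 0.40 | 0.4 | 0.0384 | −0.037 | 5.7% |
| 0.40 | 0.6 | 0.0864 | −0.080 | 8.2% |
| 0.40 | 0.8 | 0.1536 | −0.133 | 14.2% |

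With no other covariates the multiplier is √47 and the last rate becomes 15.1%. Simulations gave the same range: slopes of −0.03 to −0.13 and false positives of about 5% to 15%. With family history in the model the rate was about 5%.

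**The same check in correlations.** If family history correlates a with VO2max and b with the outcome after the four covariates, the spurious correlation is a×b. If either is 0 there is no bias. At a = b = 0.2 it is 0.04 (5.8% false positives), at 0.3 it is 0.09 (9.1%), and at 0.4 it is 0.16 (18.5%). The last case is stronger than any row of the table, where a = b = √(v/(1+v)) is at most about 0.36. For scale, 50 children with four covariates detect a partial correlation of about 0.40 with 80% power.

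**If BMI percentile carries half of each shift.** The shift left after adjustment is roughly d/2, so v falls to a quarter. At p = 0.40 and d = 0.8, v = 0.0384 and the slope is −0.037. Across the grid a simulation gave −0.01 to −0.04, with false positives of 5% to 6%.

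**Mediated share.** Assume a true indirect effect of −0.16 and a total effect of −0.36, a share of 44%. Let family history shift CRF and the outcome by 0.6 SD and leave it out of the model.

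- No direct effect on the mediator: the indirect effect stays at −0.16. The total becomes −0.36−0.063 = −0.423 (p = 0.25) or −0.36−0.080 = −0.440 (p = 0.40). The share falls to 38% or 36%.
- A 0.2 SD shift in the mediator: the share is 40% to 41%.
- A 0.6 SD shift in the mediator: the share is about 48%.

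**Cost of adjusting.** Residual degrees of freedom go from 50−6 = 44 to 43. The partial correlation detectable at 80% power moves from 0.403 to 0.407. The standard error is multiplied by √(1/(1−a²)) × √(44/43), which is 1.012 at a = 0 and 1.060 at a = 0.3. This is before any gain from outcome variance that family history explains; in the simulated scenarios the net rise was about 1% to 2%.

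**The case against.** The strongest reply is that the documents never link diabetes family history to CRF or to fat oxidation. The Background says only that CRF is partly genetic, not that it shares inheritance with diabetes risk. Bias requires family history to relate to both CRF (or the mediator) and the outcome after the four covariates, and BMI percentile is a plausible route for part of that risk. This stands. A reader might infer that inherited risk will be credited to CRF, but the documents support only that it may be.

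A reader might also infer that the mediated share is inflated along with the total effect. That does not follow. In the example the share fell when family history did not act on the mediator and rose only when it acted on it strongly.

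It is also fair to say that this is a 50-child pilot, that nothing in the plan forbids further covariates, and that demographics and past medical history from the same questionnaire are likewise assigned to no model. Collecting an item for description is not an error. Even so, an unstated use leaves the choice to include or drop family history open until results are seen.

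Finally, family history is a crude proxy. It may partly reflect a shared household, and a yes/no answer ignores degree of relative and diabetes type. The 5% adjusted rate holds only because the simulation treats it as the whole confounder, measured without error.

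**Conclusion.** The point holds as a modest, inexpensive improvement. A measured candidate confounder that precedes the exposure is left out of every model, in an analysis where the exposure is observed and mediation is claimed.

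Under the assumed prevalences and shifts, the slope bias is about −0.03 to −0.13 SD per SD, and false positives are about 5% to 15% instead of 5%. At the middle shift of 0.6 SD the rate is 7% to 8%. For each assumed shift these are upper figures, since they let BMI percentile absorb nothing; if it carries half, the rate is 5% to 6%. If family history is unrelated to CRF or to the outcome, there is no bias. The documents give no value that narrows this range, and they do not settle which way the mediated share would move.

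**What to change.** In Section 2.0, add diabetes family history (yes/no, from the existing questionnaire) as a prespecified covariate in the Aim 2 mixed models, the Aim 3 regressions and both equations of the mediation analyses. A prespecified sensitivity adjustment in the same models is the minimum. State which relatives count, which type of diabetes counts, and how unknown or missing answers are handled. Say explicitly which covariates the Aim 3 total-effect regression carries. If the item is meant only for description, say so. Because control will be partial, report a sensitivity analysis for unmeasured confounding with the mediation results.

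The cost is one degree of freedom and a standard error about 1% to 6% larger. No new data collection is needed.

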**Between Study Visit 1 and 2**

Between Study Visit 1 and 2, all participants will receive an Actigraph GT9X triaxial accelerometer to objectively assess habitual physical activity for at least seven days. All participants will complete three dietary recalls detailing foods eaten. The timeframe between Study Visit 1 and 2 will be ~7-14 days.

**Study Visit 2:** Participants will arrive at the Clinical Research Unit in Faulkner Building 4M at the Main Campus of DHMC after an overnight fast ( $\geq 12$  hours). Upon arrival, the CRC or other study team member will collect accelerometers and data will be exported via ActiLife software. A RN will place an intravenous line to collect blood sampling throughout the acute meal challenge. The CRC or other study team member will mix and provide the HF-challenge, containing approximately 15% calories from carbohydrates, 15% calories from protein, and 70% calories from fat. Participants will receive a survey identifying their taste preference for the HF shake. Blood sampling will occur prior to the consumption of the HF challenge and 30, 60, 120, and 180 minutes after the consumption of the HF challenge. The CRC or other study team member will collect a 24-hour dietary recall of the previous day. After drinking the HF challenge, the CRC or other team member will collect a brief survey about the taste preference of the HF challenge. Metabolomics and assays for gene expression will be conducted across the time-course.

Participants will be compensated \$75 for the completion of the study visit.

PROTOCOL TITLE: Metabolic Response to a High-Fat Challenge in Children and Adolescents.  
**Protocol – One Study Visit**

Participants will receive an Actigraph GT9X triaxial accelerometer to objectively assess habitual physical activity for at least seven days. All participants will complete three dietary recalls detailing foods eaten.

Participants will arrive at the Clinical Research Unit in Faulkner Building 4M at the Main Campus of Dartmouth Hitchcock Medical Center (DHMC) after an overnight fast ( $\geq 12$  hours). Consent and assent documents will be available to re-read prior to study visit. The CRC or other study team member will collect weight, height, blood pressure, waist circumference, and hip circumference. Each participant will have body composition analyzed using bioelectrical-impedance analyses (BIA). Parents/Guardians will fill out electronic questionnaires about demographics, diabetes family history, and past medical history. Children will fill out electronic questionnaires about puberty status measured by Tanner's Stages.

A RN will place an intravenous line to collect blood sampling throughout the acute meal challenge. The CRC or other study team member will mix and provide the HF-challenge, containing approximately 15% calories from carbohydrates, 15% calories from protein, and 70% calories from fat. Participants will receive a survey identifying their taste preference for the HF shake. Blood sampling will occur prior to the consumption of the HF challenge and 30, 60, 120, and 180 minutes after the consumption of the HF challenge. The CRC or other study team member will collect a 24-hour dietary recall of the previous day. After drinking the HF challenge, the CRC or other team member will collect a brief survey about the taste preference of the HF challenge. Metabolomics and assays for gene expression will be conducted across the time-course.

Participants will be compensated \$75 for the completion of the study visit.

## **Assessment Details**

### **Physical Assessment**

A physical examination will then be conducted, which includes measurement of height, weight, blood pressure, waist circumference, and hip circumference. Measurements will be collected by the CRC or other member of the research team.

### **Bioelectrical Impedance Analysis**

BIA (SECA, Hamburg, Germany) is a non-invasive test providing the measurement of fat and lean mass in each participant. A weak non-detectable electric current will flow through the body and the voltage is measured to calculate impedance (resistance) of the body. Body compartments (fat, bone, lean mass, water) provide differential resistance to the electrical current flow, allowing for an estimation of lean and fat mass.

### **Maximal Aerobic Capacity Test**

PROTOCOL TITLE: Metabolic Response to a High-Fat Challenge in Children and Adolescents.

The maximal aerobic capacity test will be performed by the expert staff of the Cardiology Unit, including an exercise physiologist, with supervision provided as needed by [name] and CRC. Participants will be acclimated to the treadmill prior to procedure.

Stress testing will use the Bruce Protocol (30), a treadmill multistage incremental protocol, increasing both the elevation and speed over a duration of time. Stage 1 starts at 10% grade and a 1.7 mph walking pace. In each subsequent stage, the grade is increased by 2% and the speed by either 0.8 or 0.9 mph until the subject is exhausted. Stage levels increase every 3 minutes.

Participants will wear a mouthpiece to allow for the measurement of oxygen consumption and carbon dioxide emission. Participants will wear a heart rate monitor around their chest to continuously monitor heart rate.  $\text{VO}_2$  peak is reached when oxygen consumption remains at steady state despite the increased workload. Participants will complete the test until they claim maximum exercise and exhaustion. Staff members will provide the same encouragement to all participants, to help them differentiate between exercise capacity constraints and lack of cooperation in exercise testing. The test will stop immediately if there is an emergency, if the subject fails to conform to the protocol, or if the subject experiences signs of discomfort.

We will adhere to the absolute and relative indications for termination of an exercise test which include the following Absolute Contraindications: moderate to severe angina, increasing nervous system symptoms (e.g. ataxia, dizziness, or near syncope), signs of poor perfusion (cyanosis or pallor), or subject's desire to stop and the following Relative Contraindications: increasing chest pain or fatigue, shortness of breath, wheezing, leg cramps, or claudication.

Previous studies have found success in the incorporation of this protocol in pediatric research (31). Additional details on clinical stress testing in the pediatric age group are provided by the AHA (32).

When conducting statistical analyses, a respiratory exchange ratio, the ratio between metabolic production of carbon dioxide and the uptake of oxygen,  $\geq 1$  will serve as an indicator that the participant was nearing exhaustion, rather than stopping prematurely.

### **Submaximal Aerobic Capacity Test**

To estimate submaximal aerobic capacity, participants will undergo a 6-minute walk test (6MWT), where distance walked is measured using a rolling measuring wheel. This test is practical and low-tech, requiring a pre-measured hallway (20-30 meters) and allowing participants to dictate their own intensity of exercise and rest during the test. The information gained from the 6MWT is not considered a replacement for a maximum cardiorespiratory fitness test, however, strong correlations have been observed (33). Participants will be instructed to walk as far as possible in 6 minutes, back and forth in a pre-measured hallway. Environmental factors will be standardized in the test facility and all participants will be encouraged to wear comfortable clothing and appropriate shoes for walking. The protocol and encouragement during

PROTOCOL TITLE: Metabolic Response to a High-Fat Challenge in Children and Adolescents. the test will be in accordance with the American Thoracic Society (34). Prediction equations to estimate  $\text{VO}_2$  max will be used (33).

We anticipate funding sources to cover the expenses for a maximal aerobic capacity test, nevertheless, our protocol includes a submaximal aerobic capacity test as a low-cost estimate of  $\text{VO}_2$  peak in preparation of lack of funding. The 6MWT can be administered in hallways within DHMC, on Level 5 due to less foot traffic, by the CRC.

### **Surveys**

Parents/Guardians will be asked to fill out electronic questionnaires about demographics, diabetes family history, and past medical history. Children will be asked to fill out surveys about puberty status using the Pubertal Development Scale (35) and a taste preference survey after the high fat shake.

### **Actigraph**

Participants will be asked to wear an ActiGraph GT9X triaxial accelerometer (ActiGraph, Pensacola, FL) for at least seven days after the first study visit to objectively assess habitual physical activity. This accelerometer was chosen as it has shown to be a reliable and valid measure of habitual physical activity in children with established data acquisition and processing methods (36). Participants will wear the monitor on their non-dominant wrist during all waking hours. Participants will be asked to remove the monitor during periods of sleeping, bathing, or swimming, as well as contact sports. Staff will be available by phone or email to answer device usage questions. Participants will complete accelerometer logs, noting the time when the device was put on and taken off. Children will return the device.

Upon collection, data will be exported from the device using ActiLife software, Version 16.3.3 (ActiGraph, Pensacola, FL). The GT9X accelerometer generates a variable output voltage signal, proportional to acceleration in three orthogonal planes (vertical, anteroposterior, and mediolateral). Acceleration is converted to activity counts and stored on the device. Physical activity will be classified into sedentary behavior and light, moderate, and vigorous physical activity (37).

